7.6. ECOG Data

The Eastern Cooperative Oncology Group (ECOG) performance score (0-5) will be collected according to Schedule and Assessment Table in the protocol.

The number and percentage of patients will be summarized for each score by schedule analysis visit. A shift table presenting baseline to worst post-baseline will also be prepared.

A listing of ECOG scores for all patients including change from baseline at each planned timepoint will be provided.

7.7. NCI-PRO-CTCAE Items (Part 1 only)

NCI-PRO-CTCAE is a patient-reported outcome (PRO) measurement system developed to evaluate symptomatic toxicity in patients. Ten relevant NCI-PRO-CTCAE items which represent 6 symptomatic toxicities drawn from the CTCAE were included in this study based on the frequency of symptomatic AEs observed in early clinical data. Each AE includes up to 3 discrete questions, separately representing the frequency, severity, interference, amount and/or presence with daily activities of the event ([Table 7.3](#)). In addition, a free-text question is added as the last question to mitigate concerns for missing important symptom items.

Table 7.3 PRO-CTCAE Attributes, Item Structures, and Item Scores

Frequency	Severity	Interference	Amount	Presence / Absence
In the last 7 days, how often did you have ____?	In the last 7 days, what was the severity of your ____ at its worst?	In the last 7 days, how much did ____ interfere with your usual or daily activities?	In the last 7 days, did you have any ____?	In the last 7 days, did you have any ____?

 • Never (0) • Rarely (1) • Occasionally (2) • Frequently (3) • Almost constantly (4) 	
 • None (0) • Mild (1) • Moderate (2) • Severe (3) • Very severe (4) 	
 • Not at all (0) • A little bit (1) • Somewhat (2) • Quite a bit (3) • Very much (4) 	
 • Not at all (0) • A little bit (1) • Somewhat (2) • Quite a bit (3) • Very much (4) 	
 • No (0) • Yes (1)

PRO-CTCAE responses are scored from 0 to 4 (or 0/1 for Presence/Absence). Specifically, if the response provided to the first question in a PRO-CTCAE item set is the lowest response on the scale (e.g., 'Never' for frequency, or 'None' for severity), scores for the conditionally branched PRO-CTCAE items should be scored/coded as 0 and are not to be coded as missing values.

The number and percentage of patients reporting each response category (i.e., None, Mild, Moderate, Severe, and Very severe for Severity) ratings within each PRO-CTCAE item will be

Statistical Analysis Plan for Protocol ABSK-021-301

tabulated by treatment group. To graphically visualize the PRO-CTCAE item, butterfly charts (as included in FDA's Project Patient Voice¹⁴) will be produced at each scheduled visit.

For items that are rated on a 5-point Likert scale (i.e., excluding Presence/Absence), the following displays will be prepared by treatment group:

- The raw rating and change from baseline by category will be summarized at each schedule analysis visit.
- The maximum baseline-adjusted response ratings with each PRO-CTCAE item will be summarized by treatment groups. Baseline-adjusted PRO-CTCAE values are the observed value at the visit if higher (worsen) than the baseline value, and 0 otherwise.

Patient disposition for each PRO-CTCAE item will be tabulated and plotted based on completion rate which will be calculated where the denominator is the number of patients expected to complete the PRO measure at the designated PRO assessment timepoint. Summaries for completion rate and missing data rate will include reasons for missing data.

In addition, summary tables and corresponding plots will provide for individual item and/or summary scores, as appropriate.

7.8. Other Safety Assessments

Echocardiography/ MUGA will be summarized by treatment groups. Observed values and changes from baseline for continuous variables will be summarized by treatment groups ([Section 7.1](#)) for each scheduled analysis visit, overall maximum and minimum post-baseline during on-treatment period, and last-value-on-treatment.

Number and percentage of patients will be summarized for echocardiography/MUGA overall interpretation by schedule analysis visit.

The pregnancy test will be listed.

8. PHARMACOKINETIC DATA ANALYSES

Pharmacokinetics will be evaluated for the pharmacokinetic analysis set and conducted in randomized ABSK021 treatment group and placebo switched to ABSK021 treatment group under the guidance of Abbisko Clinical Pharmacology Group. Below analysis will be performed for ABSK021 and its metabolite.

Concentration-time data will be listed to include both actual and planned time points, deviation time between actual and planned time, and actual blood sampling time relative to dose.

Descriptive summary of concentrations-time data will be provided for each nominal time including number of patients with available data (n), number of subjects with imputed value (BQL assigned to zero); arithmetic mean (Mean), standard deviation (SD); coefficient of variation (%CV); median (Median), maximum (Max), minimum (Min) and geometric mean (Geo Mean), geometric %CV.

PK concentrations will also be presented in the by-patient data listings.

Statistical Analysis Plan for Protocol ABSK-021-301

9. CHANGE FROM ANALYSIS PLANNED IN PROTOCOL

Plan specified in protocol	Change in SAP and rationales
NA	NA

11. APPENDICES

11.1. Appendix 1: Partial Date Imputation Rule

Completely Missing or Partially Missing AE Date

AE start date

- If the start date has month and year but day is missing, the first dose date will be used if the month and year is the same as the first dose date and the end date is greater than the first dose or completely missing, otherwise, the first day of the month will be used.
- If the start date has year, but day and month are missing, then the first dose date will be used if the year is the same as the first dose date and the end date is greater than the first dose or completely missing, otherwise 1st January will be used.
- If the start date is completely missing, then it will be imputed as the first dose date of study drug if the end date is equal or greater than the first dose date or completely missing, otherwise ICF signed date will be used.

After imputation, the imputed start date will be compared with ICF signed date. If the imputed start date is earlier than ICF signed date, the start date will be imputed with ICF signed date instead.

AE end date

- If the end date has month and year but day is missing, the last day of the month will be used.
- If the end date has year, but day and month are missing, the 31st December will be used.
- If the end date is completely missing, the last dose date + 30 days will be used if the AE occurs or worsens after the first dose date of study drug; If the AE occurs prior to the first dose date of study drug, the end date will be imputed with the first dose date.

After the imputation, the imputed AE end date will be compared against the AE start date and the death date for patients who died. If the imputed AE end date is earlier than the start date, then the AE start date will be used to impute the end date instead. If the date is later than the death date, the date of death will be used to impute the end date instead.

Completely Missing or Partially Missing Medication/Non-Medication Therapy Date

Start date

Statistical Analysis Plan for Protocol ABSK-021-301

-
- If the start date has month and year but day is missing, the first dose date will be used if the month and year is the same as the first dose date and the end date is greater than the first dose or completely missing, otherwise, the first day of the month will be used.
 - If the start date has year, but day and month are missing, then the first dose date will be used if the year is the same as the first dose date and the end date is greater than the first dose or completely missing, otherwise 1st January will be used.
 - If the start date is completely missing, then it will be imputed as the first dose date of study drug if the end date is equal or greater than the first dose date or completely missing, otherwise ICF signed date will be used.

After the imputation, the imputed start date will be compared with ICF signed date, if available. If the imputed start date is earlier than ICF signed date and the collected partial part is the same as ICF signed date, the start date will be imputed with ICF signed date instead.

End date

- If the end date has month and year but day is missing, the last day of the month will be used.
- If the end date has year, but day and month are missing, the 31st December will be used.
- If the end date is completely missing, the last dose date + 30 days will be used if the medication/non-medication therapy is taken after the first dose date of study drug; If it is taken prior to the first dose date of study drug, the end date will be imputed with the first dose date.

After the imputation, the imputed end date will be compared against the start date and the death date for patients who died. If the imputed end date is earlier than the start date, then the start date will be used to impute the end date instead. If the date is later than the death date, the date of death will be used to impute the end date instead.

Partially Missing Initial Diagnosis Date

- If the date has month and year but day is missing, the first day of the month will be used.
- If the date has year, but day and month are missing, 1st January will be used.

Completely Missing or Partially Missing Subsequent Anti-Cancer Therapy Date

- If the start date has month and year but day is missing, the first day of the month will be used if the partial part is later than the earliest of the end date and the later one among the first PD date + 1 and the last dose date +1, or the last day of the month will be used if the partial part is earlier than the earliest of the end date and the later one among the first PD date + 1 and the last dose date +1.
 - If the start date has year, but day and month are missing, 1st January will be used if the partial part is later than the earliest of the end date and the later one among the first PD date + 1 and the last dose date +1, or 31st December will be used if the partial part is earlier than the earliest of the end date and the later one among the first PD date + 1 and the last dose date +1.
-

Statistical Analysis Plan for Protocol ABSK-021-301

- If the start date is completely missing or the partial part is as same as the earliest of the end date and the later one among the first PD date + 1 and the last dose date +1, then it will be imputed as the earliest of the end date and the later one among the first PD date + 1 and the last dose date +1.

Completely Missing or Partially Missing Death Date

- If the date has month and year but day is missing, the first day of the month will be used if the partial part is greater than last survival date.
- If the date has year, but day and month are missing, 1st January will be used if the partial part is greater than last survival date.
- If the date is completely missing or the partial part is as same as the last survival date, then use the last survival date + 1 to impute.

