5.5. Prior, Concomitant and Subsequent Therapy

5.5.1. Definition and Classification

Prior and concomitant and subsequent therapy includes any medications for treating both cancer and non-cancer conditions, surgeries, and radiotherapies that patients received prior to the study start, during study treatment and throughout study follow-up period. Medications will be coded to Anatomical Therapeutic Classification (ATC) and preferred name (PN) using the latest version of World Health Organization Drug Dictionary (WHODD). Non-medication therapies will be coded using MedDRA.

Prior therapies are those medications, surgeries and radiotherapies received prior to the first dose of the study drug and ending before the first study drug dose of Part 1. Concomitant therapies are defined as of those were started on or after the first dose of the study drug but prior to the last dose of the study drug at the time of data cut-off + 30 days or started prior to the study drug and were ongoing during the treatment period. Subsequent anti-cancer therapies are those that ~~were~~ started after the last dose of the study drug. Medications, surgeries and radiotherapies with incomplete start and/or end dates will be imputed for classification of prior, concomitant and subsequent according to [Appendix 1](#). Those with incomplete start and/or end dates will be assumed to be concomitant if it cannot be shown that the medication, surgery or radiation therapy was not taken during the treatment period. For any incomplete onset or end date, the imputed date and raw date will be listed.

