5.5.2. Prior Anti-Cancer Therapy

The number and percentage of patients with any prior systemic anti-cancer therapy, intent, line of therapy, type of therapy, the best response, reason for discontinuation and disease progression or recurrence will be summarized by treatment group for the ITT analysis set. The duration of last prior systematic therapy and time from the date of last prior systemic therapy to the first dose of study drug may be descriptively summarized.

Statistical Analysis Plan for Protocol ABSK-021-301

The number and percentage of patients under different number of prior surgery (i.e., none, ≥ 1 , ≥ 2 , ≥ 3 etc.) and patients with or without radiation therapy will be summarized by treatment group and overall.

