6.3.6. Subgroup Analyses

Subgroup analyses for the primary BIRC-25-Week ORR will also be performed within the following subgroups to assess whether study drug exhibits a consistent treatment effect across each of these subgroups.

- Age Group (< 40years, ≥ 40years, ≥ 40 - < 65 years, ≥ 65 years)
- Sex (Female vs. Male)
- Region Category 1 (China vs. ex-China)
- Region Category 2 (China vs. North American vs. EU)
- Race Category 1 (Asian vs. non-Asian)
- Race Category 2 (Caucasian, non-Caucasian)
- Ethnicity (Hispanic or Latino vs. Not Hispanic or Latino)
- Lower extremity tumors vs. upper extremity tumors
- Knee vs. Others
- TCGT type (localized-type vs. Diffuse-type)
- ECOG PS (0 vs.1)

Statistical Analysis Plan for Protocol ABSK-021-301

- Number of prior surgeries (0 vs. ≥ 1)
- Prior systemic therapy (Yes vs. No)

For each subgroup defined above, the same approach employed in the primary analysis of the primary ORR will be used. These subgroup analyses are considered exploratory in nature and will not involve adjustments for multiple comparisons. A forest plot illustrating the difference in ORR (ABSK021- Placebo) and its corresponding 95% CI (Wilson method) will be produced for each subgroup. If any subgroup contains an insufficient number (i.e. less than 5) of patients for meaningful analysis, the data for those subgroups will be presented descriptively rather than being subjected to statistical testing.

6.4. Key Secondary Efficacy Endpoints Analysis – Part 1

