6.4.5. Supportive Analyses of Key Secondary Endpoints

ROM and PROs under Different Strategy to the Intercurrent Event

For intercurrent event of receiving an alternative anti-tumor therapy (including surgery), while on treatment policy will be used for ROM and PROs as the sensitivity analyses. The similar MMRM model as the primary analysis of ROM and PROs will be used. The data after receiving an alternative anti-tumor therapy (including surgery) will not be included in the analyses.

BPI-30

A BPI-30 responder will be defined as a patient who (i) experienced a decrease of at least 30% in the mean BPI Worst Pain NRS item AND (ii) did not experience a 30% or greater increase in narcotic analgesic use, comparing data collected in concomitant medication during a 7-day period at the end of Part 1 compared with baseline values collected prior to the first dose of study treatment. Patients who do not provide data for the endpoint will be considered to be non-responders. Analgesic use will also be recorded in BPI visit and linked to concomitant medication page. If a patient didn't use analgesic medication at baseline but used it at post-baseline, it's regarded as a 30% or greater increase in narcotic analgesic use. If a patient used the same analgesic medication at baseline and post-baseline, the change in analgesic use should be calculated by the change in patients' mean analgesic use that calculated by multiplying the daily dose unit by the number of units taken, averaged by the number of days with available data in concomitant medication. If a patient used different analgesic medications at baseline and post-baseline, whether a 30% or greater increase in analgesic use will be judged by medical review case by case.

The BPI-30 responders will be summarized by treatment group based on ITT. The treatment comparison of BPI-30 will be based on Fisher's exact test.

Responder Summary of COAs (i.e., ROM and PRO) by Clinical Thresholds

Descriptive by-treatment responder summary of the COAs change from baseline at Week 25 by thresholds of clinically meaningful within-patient change will be performed, such as 5%, 6.7%, 10%, 15%, 20%, and 25% for ROM; 1 point improvement for Worst Stiffness and 3 points improvement for PROMIS-PF T-scores (Speck et al., 2020⁸), and 1 point improvement for BPI (Dworkin et al., 2008¹⁰).

Statistical Analysis Plan for Protocol ABSK-021-301

eCDF and ePDF Plots

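### SAP Appendix 1 can date a prior therapy's start after its recorded end, or move a partly recorded end forward to consent, which distorts the prior-therapy summaries

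*SAP*

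**What the plan says.** SAP 5.5.1 takes medicines, surgeries and radiotherapies together and sends them to Appendix 1: "Medications, surgeries and radiotherapies with incomplete start and/or end dates will be imputed for classification of prior, concomitant and subsequent". A therapy is prior if it was received before the first dose and also ended before the first Part 1 dose. A record with incomplete dates counts as concomitant unless it can be shown that the therapy was not given on treatment.

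Appendix 1 (SAP 11.1), under medication and non-medication therapy dates, then gives these rules:

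- Start wholly missing: "If the start date is completely missing, then it will be imputed as the first dose date of study drug" if the end is "equal or greater than the first dose date or completely missing, otherwise ICF signed date will be used".
- End partly recorded: last day of the month, or 31 December.
- End wholly missing: last dose plus 30 days if the therapy is taken after first dose. Otherwise, "If it is taken prior to the first dose date of study drug, the end date will be imputed with the first dose date".
- Consistency check: an imputed end that falls before the start is replaced by the start. No check works the other way, so an imputed start is never limited by the end.

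The dates matter in SAP 5.5.2, which says these may be summarised: "The duration of last prior systematic therapy and time from the date of last prior systemic therapy to the first dose". That section also tabulates the number of prior surgeries. SAP 6.3.6 has a subgroup entry beginning "Number of prior surgeries (0 vs. ≥ 1", and SAP 6.4.6 carries the subgroups over to the key secondary endpoints.

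**The concern.** The completely-missing-start rule for therapies is the same as the one for adverse events a page earlier in Appendix 1. For adverse events the consent-date fallback is natural, because they are collected only from consent (Protocol 6.4.11). Therapies can end years before consent. The later comparison with the consent date was adapted for therapies (it now also requires the recorded part of the date to match), but the completely-missing branch was left as it stood.

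The exposed group is prior anti-tumour therapy. Ordinary prior medicines are collected only from 28 days before randomization (Protocol 6.4.10), which leaves little room for the error. At stake are negative or one-day treatment durations, times since last therapy that look like washout breaches, and possibly surgeries missing from the prior-surgery count.

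**Working it through.** **Where prior anti-tumour therapy lies relative to consent.** Exclusion 8 bars it within 4 weeks before randomization. Screening, including consent, is to be completed within 28 days before randomization (Protocol Table 1, footnote 1). A therapy that satisfies Exclusion 8 has therefore normally ended by consent. An extended screening period could be an exception.

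**Test records.** The documents give no figure here, so I applied the rules to assumed dates: consent 20 August 2023 and first dose 15 September 2023, 26 days apart. Duration is end − start + 1; the SAP states no formula for therapies. I take a partial end to be completed before it is compared with first dose; the SAP does not state the order.

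1. *Start missing, end recorded as 10 March 2022.* The end precedes first dose, so the start becomes 20 August 2023, which is 528 days after the end. Duration = −528 + 1 = −527 days. The end is a recorded date, so the check does not act. The record still ends before first dose and stays prior. Time since last therapy is 528 + 26 = 554 days, which is correct.
2. *Start missing, end recorded as March 2022.* The end is completed to 31 March 2022 and the start becomes 20 August 2023. The check then replaces the end with 20 August 2023, contradicting the recorded month and year. Duration = 1 day. Time since last therapy is 26 days, against 533 from 31 March 2022.
3. *Start missing, end recorded as 2022.* The end goes to 31 December 2022 and then to 20 August 2023. Duration = 1 day. Time since last therapy is 26 days, against 258 from 31 December 2022.
4. *Surgery in 2019 (year only), end missing.* The start stays at 1 January 2019. The end becomes the first-dose date, which is not before the first dose, so the record literally fails the definition of prior.
5. *Surgery with 2019 as both start and end.* The record is correctly prior.

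The start-after-end gap is the whole interval from end to consent. A drug that ended on 15 March 2021 with consent on 1 June 2024 gives 1,096 + 78 = 1,174 days.

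**A ceiling in records 2 and 3.** Consent is at most 28 days before randomization in the ordinary screening window, and first dose is within 3 days of randomization (Protocol 5.6). The imputed time since last therapy is therefore at most 28 + 3 = 31 days, whatever the true interval. In the example, 26 days before first dose is at most 26 days before randomization. That is under 4 weeks, so the record looks like an Exclusion 8 breach that did not occur.

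**The case against.** The best defence is that little depends on this rule, and most of that stands.

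- *Classification in the start-after-end case.* The record remains prior, so prior systemic therapy yes/no and its subgroup do not change. If the end is fully recorded, time since last therapy is also right. The SAP 5.5.2 duration summary is optional, and that section does not say whether it uses imputed dates.
- *Surgery.* A reader might infer that old surgeries move to Day 1 and patients fall into the wrong prior-surgery level. The documents do not establish this. A surgery with an earlier recorded year keeps a start in that year. A Day 1 start needs a wholly missing date or a partial one matching first dose ("the first dose date will be used if the year is the same as the first dose date and the end date is" after first dose or missing). Prior anti-tumour therapy is collected at screening, so the cannot-be-shown clause in SAP 5.5.1 may rescue these records. Neither 5.5.2 nor 6.3.6 says the count is built from imputed dates. However, no rule says that screening history is sufficient proof.
- *BPI-30.* A reader might infer that a long-standing analgesic with an unknown start is dated Day 1, read as new use and so "regarded as a 30% or greater increase in narcotic analgesic use", making the patient a non-responder. SAP 6.4.5 also records analgesic use at the BPI visit and does not tie baseline use to Appendix 1 dates. Nor does the end rule clearly stop a continuing analgesic on Day 1, because such a medicine also fits the branch for therapies taken after first dose. The link to the concomitant medication page leaves the source unclear, but an error is not shown. Nothing in the documents supports putting a size on any loss of effect.

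What the defence does not remove is that the start rule produces impossible or contradicted dates. SAP 5.5.1 requires imputed dates to be listed beside the raw ones, so these would appear in the listings even if no summary used them.

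**Conclusion.** The rule is wrong as written for therapies with no start date and an end before consent. A fully recorded end gives a negative duration. A partly recorded end is overwritten by the consent date, leaving a one-day duration and a time since last therapy of at most 31 days under ordinary screening. The missing-end rule also conflicts, read literally, with the definition of prior for old surgeries, though SAP 5.5.1 may rescue them.

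The consequence is limited. The exposed outputs are the optional SAP 5.5.2 summaries, provided imputed dates feed them, and possibly the prior-surgery tabulation and exploratory subgroup. The main primary and key secondary analyses are unaffected, and BPI-30 is a matter for clarification. The number of affected records is unknown, and the day counts above rest on assumed consent and dosing dates.

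**What to change.** Amend Appendix 1, with short cross-references in SAP 5.5.1 and 6.4.5:

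- Never impute a start later than a known or partly known end, and never change a recorded part of an end date.
- Classify therapies entered in the screening prior-therapy history as prior whatever the imputed date, and set a missing procedure end date to its start date.
- State that a medicine recorded as ongoing takes the last-dose-plus-30-days branch, and that BPI-30 baseline analgesic use comes from the BPI-visit record, not from Appendix 1 dates.

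I would not go further and date every unknown analgesic start before the baseline window, because that could hide genuine new use on study.

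The cost is SAP wording and programming. No new data are needed if the case report form identifies prior-therapy records and ongoing medicines; the form is not among the documents, so this should be confirmed. Settling it before the Part 1 database lock avoids ad hoc decisions after unblinding.
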